1. PURPOSE OF STUDY

a. Brief Summary

Untreated Pain Catastrophizing can lead to increased opioid use and facilitate the risk for misuse and overuse of medications, particularly when surgery and pharmacologics are the focal medical care plan. Despite critical need, there are no targeted interventions that efficiently address the key psychological factors that can amplify both pain, need for opioids, and increased risk for misuse. In this project, we will attempt to address this urgent need for efficient and effective solutions. Our group has developed a 2-hour targeted, single-session pain catastrophizing class (PC-class), rooted in cognitive-behavioral therapy (CBT) approaches, aimed at reducing opioid use by reducing pain catastrophizing in chronic pain.

b. Study Objectives

This project aims to identify patients who achieve a meaningful reduction in opioid use, which will enable better characterization of treatment responders and refining opioid reduction strategies. Also, the daily data will be used characterize the mechanistic influence of catastrophizing on opioid use both on the daily-level and prospectively.

c. Rationale for Research in Humans

This research necessitates human participants because there is no equivalent animal model or non-human model to answer the study questions. The interventions are designed for human participants only.

2. STUDY PROCEDURES

a. Procedures

- i. Screening of Participants: A total of 300 male and female adult patients (ages 18-80) who meet criteria for a chronic pain condition receiving care at the Stanford Pain Management Centers will be enrolled. Recruitment efforts will include targeted emails and advertisements at Stanford's pain management clinics. Screening procedures will include a phone screening by study staff, or an in-person screening. Informed consent will either be obtained in-person during the visit, or through REDCap or on the phone with a research coordinator. All participants will have the informed consent presented to them through REDCap where they can provide their digital signature. All participants will automatically be emailed a copy of their informed consent.
- ii. Screening visit or call: During this first visit, after eligibility has been determined, we may ask participants to use a computer, handheld device like a tablet, or iOS/android phone to record their daily pain and take the full surveys at specified time points. During or after this visit or call, they may be randomized to one of the 2 class types described below, and we may contact them to inform them of their schedule. After randomization, patients will be emailed a schedule of their participation.
- iii. Pre-Class Procedures: Participants will complete an enrollment survey online using a secure, HIPAA compliant, online system (via REDCap or Qualtrics). There is a chance that patients may present with depression, as measured by the PROMIS Depression Short Form upon enrollment. Patients exhibiting signs of depression (a raw score of 33 or greater) will be provided with a list of mental health providers/resources (attached in section 16). Patients endorsing suicidality will be offered immediate assessment and will be considered ineligible and subsequently withdrawn from the study. Responses the PROMIS Depression Short Form will be assessed within one week to assure prompt response to signs of depression and suicidality.

smart phone, or through a secure website. The research team will provide participants with instruction on how to use this device or complete their questionnaires. If they are provided with a tablet or android phone, they will be asked to return these devices at the end of their study participation. Participants will also fill out questionnaires at several time points during the study: before treatment start, after-treatment, once a month during the 3 months following their class, and once more 6 months after the class, and one last time 12 months after the class. These questions may take approximately 30-60 minutes to complete and include questions about their symptoms, mood, function, medication use, and other treatments being used. This may occur via secure web survey, regular mail, the handheld device, or by phone interview.

The PROMIS Depression Short Form will be administered for the pre-class, 3-, 6-, and 12-month questionnaires detailed above. PROMIS Depression Short Form scores will be monitored in real time and suicidality will be assessed with the same procedures as with the enrollment survey for these following questionnaires.

Patients will be sent thank you emails with enclosed amazon codes for compensation.

Additional visits to our lab may be scheduled in order to help participants with downloading the data from their handheld device, should you need such help.

b. Procedure Risks

All members of the study team have been trained to conduct the research procedures in the safest manner possible. There are no known risks to completing the questionnaires or undergoing proposed interventions. Participants will be informed that they have the right to refuse to answer questions and they can withdraw from the study at any time.

c. Use of Deception in the Study

Deception will not be used.

d. Use of Audio and Video Recordings

Recording for the treatment sessions may occur so that the study team can review the session to confirm instructor adherence to the treatment protocols. After treatment fidelity has been confirmed, recordings will be permanently deleted.

e. Alternative Procedures or Courses of Treatment

No standard treatment is being withheld. Participants are encouraged to continue with their current course of treatment for their pain under the care of their regular physician. Participant's alternative is to not participate.

f. Will it be possible to continue the more (most) appropriate therapy for the participant(s) after the conclusion of the study?

Participants are free to pursue the treatment of their choice at any time after the study. If participants are exhibiting signs of depression (PROMIS depression raw score of 33 or greater), a research coordinator or study psychologist will provide the participant with a list of mental health resources/providers attached in section 16.

g. Study Endpoint(s)

Each participant will meet the study endpoint once he/she completes the last set of questionnaires at the final time point. The study will end once the target enrollment is reached.

3. BACKGROUND

a. Past Experimental and/or Clinical Findings

There is an urgent need to better integrate targeted effective treatment for opioid use by reducing pain catastrophizing. Cognitive behavior therapy (CBT) has demonstrated preliminary promising results for opioid-treated chronic pain, with reductions in opioid use (1), misuse (1), aberrant opioid-related behaviors (3), and discontinuation of opioid use by four patient participants in a small pre-post clinical trial (4). Similarly, pain catastrophizing is typically treated with 8-sessions of group Cognitive Behavioral Therapy (pain CBT; 16 hours of treatment time) (5), and the efficacy of pain CBT appears to be mediated by changes in pain catastrophizing (6-9). However, while existing pain CBT modalities are effective, patients incur many barriers with the typical 6-8 sessions of treatment including substantial cost, time and travel burden, lack of skilled clinicians, insurance coverage, and copayments (10-12). These barriers to care reduce patient access and may foster reliance on pharmacologic and interventional modalities, thereby illustrating the need to develop targeted, efficient, low-cost treatment strategies that will dismantle current barriers and improve patient access to care and ultimately treatment outcomes. In addition, an identified lack of skilled pain psychologists in the U.S. has underscored the need to develop effective treatment approaches that are highly efficient (13). For this proposal, we aim to utilize the single session, 2-hour patient class for the first time to focially target opioid use through reducing pain catastrophizing. The class is rooted in cognitive behavioral principles, includes education about opioid reduction and pain management, in addition to specific skills acquisition. Participants develop personalized plans to identify and stop pain catastrophizing using a variety of psychological tools, including an already developed smartphone audio app (Relaxation Response). We aim to give all patients rapid access to low-risk care that empowers them to self-manage their pain and reduce reliance on opioids.

b. Findings from Past Animal Experiments

N/A

4. RADIOISOPES OR RADIATION MACHINES

a. Standard of Care (SOC) Procedures

Identify Week/Month of study	Name of Exam	Identify if SOC or Research
N/A	N/A	N/A

b. Radioisopes

i. Radionuclide(s) and chemical form(s)

N/A

ii. Total number of times the radioisotope and activity will be administered (mCi) and the route of administration for a typical study participant

N/A

iii. If not FDA approved: dosimetry information and source documents (package insert, Medical Internal Radiation Dose [MIRD] calculation, and peer reviewed literature)

N/A

c. Radiation Machines – Diagnostic Procedures

i. Examination description (well-established procedures)

N/A

ii. Total number of times each procedure will be performed (typical study participant)

N/A

iii. Setup and techniques to support dose modeling

N/A

iv. FDA status of the machine and information on dose modeling (if procedure is not well-established)

N/A

d. Radiation Machines – Therapeutic Procedures

- i. Area treated, dose per fraction/number of fractions, performed as part of normal clinical management or due to research participation (well-established procedures)

N/A

- ii. FDA status of the machine, basis for dosimetry, area treated, dose per fraction and number of fractions (if procedure is not well-established)

N/A

5. DEVICES USED IN THE STUDY

a. Investigational Devices (Including Commercial Devices Used Off-Label)

N/A

b. IDE Exempt Devices

N/A

6. DRUGS, BIOLOGICS, REAGENTS, OR CHEMICALS USED IN THE STUDY

a. Investigational Drugs, Biologics, Reagents, or Chemicals

N/A

b. Commercial Drugs, Biologics, Reagents, or Chemicals

N/A

7. DISINFECTION PROCEDURES FOR MEDICAL EQUIPMENT USED ON BOTH HUMANS AND ANIMALS

N/A

8. PARTICIPANT POPULATION

a. Planned Enrollment

We plan to enroll up to 300 patients with chronic pain, all of them at Stanford. Sample Size Estimation was conducted: a sample size of 116 completers (58 per group) was estimated to produce 80% power to

detect medium-large treatment effects on the primary outcome (opioid use). The main effect of PC treatment on opioid use will be compared against the HE control condition using a 2-samples t-test. However, given the attrition rate in behavioral treatments, namely pain CBT literature, is typically 18-25%, we plan to over enroll to account for attrition.

b. Age, Gender, and Ethnic Background

Men and women, ages 18-80 of any race or ethnicity may be recruited.

c. Vulnerable Populations

None

d. Rationale for Exclusion of Certain Populations

This study is looking at a class structured for an adult population; therefore, children will not be included.

e. Stanford Populations

We expect this research to be accessible to any adult patient with chronic pain who is taking opioid medication, some of whom may be students, employees, or lab personnel. We will afford them the same opportunity as any other participant.

f. Healthy Volunteers

N/A

g. Recruitment Details

We may be recruiting through our existing database of patients who are interested and willing to be contacted about future studies, through physician referrals for the Stanford Pain Management Center and outside providers, and through internet advertising using sites such as Craigslist, Google, and social media ads. Recruitment may also be done through an online survey available to interested potential participants through our study-specific online screening form (attached in Section 16), through our lab website (protocol 33436), through the National Pain Report, and from screen failures or participants who will conclude their future participation in other studies taking place in the lab. Additional recruitment avenues for this project may include:

- Hardcopy and screen advertising with flyers, brochures, and postcards at physicians' offices and community locations
- Online and Social Media Ads (e.g., Facebook, Stanford Report, Craigslist, Reddit, lab website) - Newspaper Ads
- Radio Ads
- Research networking sites such as Researchmatch.org and patientslikeme.com - Registration on Clinicaltrials.gov We are not planning to mail any advertisements.

h. Eligibility Criteria

i. Inclusion criteria:

- 1) 18-80 years of age
- 2) Diagnosis of chronic non-cancer pain (> 3 months in duration)
- 3) Currently using prescription opioids ≥ 10 mg morphine equivalent daily dose (MEDD) for ≥ 3 months
- 4) Ability and willingness to complete study procedures

ii. Exclusion Criteria

- 1) Open litigation regarding a medical condition
- 2) Inability to provide informed consent and complete study procedures
- 3) Active suicidality

i. Screening Procedures

Potential participants will be screened using the attached phone script to determine eligibility prior to consent. We are obtaining a limited waiver of authorization to collect initial eligibility information in the phone screen, which may include questions about their pain and opioid use.

j. Participation in Multiple Protocols

Participants will be asked whether they are enrolled in any other research studies. If another study's procedures interfere with our own or places the subject at increased risk, he/she will not be enrolled in our study.

k. Payments to Participants

Participants will be compensated \$25 for completing assessments at enrollment, baseline, and at 1, 6 and 12-month time points, and \$35 at 3-month follow-up. Therefore, total potential compensation per participant is \$160.

1. Costs to Participants

No costs will be charged to the participants.

m. Planned Duration of the Study

The entire study is estimated to take 5 years. For each participant:

- (i) Phone screening will take about 10 minutes.
- (ii) Active participation in the intervention is one session, with 12 months of post-treatment follow-up. There may be additional wait time before treatment starts.
- (iii) Data analysis is expected to take 2-3 years.

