### **Statistical Analysis Plan**

To test the hypothesis that the Empowered Relief class would lead to greater reductions in opioid use than Health Education class, the primary outcome/endpoint was designated as reduction in opioid use as represented by morphine equivalent dose (MED) at 3 months. Within-participant differences from baseline to 3 months in MED was calculated. As the MED scores and difference scores were not normally distributed, the comparison between difference scores in the Empowered Relief arm and the Health Education arm utilized a Mann-Whitney U test (primary outcome).

We then compared the proportion of participants reaching clinically significant reductions in MED between the Empowered Relief and Health Education groups. Clinically minimal reduction is defined as >15% reduction in opioid use. We quantified absolute opioid reduction in addition to percent change reduction within subject and between groups. Finally, we quantified percent achieving each group threshold for importance of change (15%, 30%, and 50% as minimally, moderately, and substantially important change scores, respectively).

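### Entry sets a minimum opioid dose but not a stable one, so tapers already under way add noise to the primary comparison and blur who counts as a responder

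*Protocol*

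**What the plan says.** **Entry.** Protocol section 8h, inclusion criterion 3, reads "Currently using prescription opioids ≥ 10 mg morphine equivalent daily dose (MEDD) for ≥ 3 months". The three months fix how long the person has been at or above the floor, not whether the dose was steady. The first exclusion is "Open litigation regarding a medical condition"; the other two concern ability to consent or complete procedures, and suicidality. None concerns a recent or planned dose change.

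**Care during the trial.** Section 2e says "Participants are encouraged to continue with their current course of treatment for their pain under the care of their regular physician". This applies to both arms. Section 8m adds "There may be additional wait time before treatment starts", with no length given.

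**Endpoint.** The SAP states "Within-participant differences from baseline to 3 months in MED was calculated" and compares the arms by a Mann-Whitney U test, naming no stratum or covariate. On responders it states "Clinically minimal reduction is defined as >15% reduction in opioid use", then adds thresholds of 30% and 50%. A fall in dose counts whatever its cause.

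**Objective.** Section 1b opens with "This project aims to identify patients who achieve a meaningful reduction in opioid use", so that treatment responders can be better characterised.

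**The concern.** Someone half-way through a taper agreed with the prescriber, and still above 10 mg, meets criterion 3. So does someone whose taper is due to start next month. Either dose can fall between baseline and month 3 regardless of the class attended. If baseline is taken before a wait for the class, part of the fall can even come before the class.

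Three things are at stake.

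- **Precision.** A mix of tapering and non-tapering participants widens the spread of the MED differences, and an unstratified rank test carries that spread as noise.
- **Within-arm rates.** The 15%, 30% and 50% proportions are raised in both arms by reductions that would have happened anyway.
- **Responder labels.** Balance between arms does not help when individuals are labelled as responders. A profile of responders would partly describe people who were already tapering.

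**Working it through.** **Inputs from the documents.** Section 8a gives 58 completers per group, 80% power, a two-sample t-test, attrition of 18–25% and enrolment of up to 300. The effect is described only as medium to large. No standard deviation, alpha or sidedness is given.

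**Step 1: the planning figure.** It can only be solved backwards. With two-sided alpha of 0.05 assumed, the detectable standardised difference at 58 per group is (1.960 + 0.842) × √(2/58) = 0.520, or 0.525 with the exact t distribution. I use d = 0.525. The point does not change the 116.

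**Step 2: variance.** Suppose a share q of each arm is tapering, with a background shift of k SD and the same class effect as everyone else. The SD grows by √(1 + q(1 − q)k²). With q = 10%:

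- k = 1: √(1 + 0.09) = 1.044; effective d = 0.525/1.044 = 0.503; t-test power falls from 80% to 77%.
- k = 2: √(1 + 0.36) = 1.166; effective d = 0.525/1.166 = 0.450; power 67%.

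With q = 20% the corresponding powers are 74% and 59%.

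**Step 3: the SAP's own test.** I simulated 58 per arm with normal errors and d = 0.525, 20,000 runs per scenario. The van Elteren test was stratified on true taper status.

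| Tapering | Shift | Mann-Whitney | van Elteren |
|---|---|---|---|
| none | – | 78% | 78% |
| 10% | 1 SD | 74% | 77% |
| 10% | 2 SD | 68% | 78% |
| 20% | 1 SD | 71% | 77% |
| 20% | 2 SD | 59% | 78% |

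Smaller simulations on the same inputs gave 74–75% and 66–68% for the unstratified test at 10% tapering. With no class effect, both tests rejected in about 5% of runs throughout. If 10% of participants misreport taper status, the stratified test gives 75% (1 SD) and 72% (2 SD) at 10% tapering. It loses less than 1 point when nobody tapers.

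**Step 4: larger enrolment.** If all 300 enrol and 25% are lost, 300 × 0.75 / 2 gives 112 per arm. The normal approximation Φ(d√(112/2) − 1.96) gives Φ(1.97) = 98% without tapers, Φ(1.80) = 96% at effective d = 0.503, and Φ(1.41) = 92% at 0.450. The loss shrinks as numbers grow.

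**Step 5: responders at more than 15%.** Assume non-taper response of 24% (Health Education) and 38% (Empowered Relief), 10% tapering and 112 per arm. Power is Φ[(Δ√n − 1.96√(2p̄(1 − p̄))) / √(p₁(1 − p₁) + p₀(1 − p₀))]. Without tapers it is 62%.

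- *Worst case: every taperer passes 15% in both arms.* Rates are 0.10 + 0.90 × 0.24 = 31.6% and 0.10 + 0.90 × 0.38 = 44.2%. The difference is 12.6 points instead of 14, and power is 49%. Taperers are 0.10/0.442 = 23% of Empowered Relief responders and 0.10/0.316 = 32% of Health Education responders.
- *Milder case: 60% of taperers pass under Health Education, with the same 14-point class effect.* Rates are 0.06 + 0.216 = 27.6% and 0.074 + 0.342 = 41.6%. The difference stays at 14 points and power is 60%. Taperers are still 0.074/0.416 = 18% and 0.06/0.276 = 22% of responders.

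So the power loss on this secondary comparison depends heavily on the assumption, while the mixing of the responder group appears in both cases.

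**The case against.** The strongest reply is that this is a randomised comparison. Tapering should balance on average, the Health Education arm carries the same background fall, and the class effect is the difference between arms. That stands. A reader might infer that tapers bias the result or are credited to the class; the documents do not support this, and the simulated type I error stays near 5%.

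A reader might also infer that tapering participants can never be separated afterwards. That goes too far. Section 2a says the questionnaires cover medication use and other treatments, section 8k pays separately for enrolment and baseline assessments, and section 8i lets the phone screen ask about opioid use. The instruments themselves are not in the documents, so some dose history may exist. What the documents do show is that the SAP uses none of it.

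Third, the share tapering is unknown, the power figures rest on assumptions, and the fall from 62% to 49% is a worst case on a secondary comparison that allows taperers no class effect. This also stands.

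Finally, taking patients on changing doses is a defensible choice for a class meant to be widely accessible. Agreed: the point concerns what is recorded and analysed, not who is admitted.

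**Conclusion.** The point holds as one of precision and interpretation, not of bias. Criterion 3 does not secure a stable dose, care continues in both arms, and neither the primary test nor the responder thresholds take account of dose trend at entry.

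At 58 per arm, d = 0.525 and 10% tapering, the primary test loses roughly 3 to 4 points of power for a 1 SD shift and about 10 for a 2 SD shift. The loss is smaller if completers approach 112 per arm and larger if tapering is more common. Normal errors, a common class effect and the 10% share are all assumptions. The effect on responder labels does not depend on sample size, and it bears directly on the stated objective. Within-arm 15%, 30% and 50% rates should be read only through the difference between arms.

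**What to change.** 1. Before randomisation, ask two questions: has the opioid dose changed in the past 3 months, and is any change already planned with the prescriber? The screening call or visit is the safer place, because section 2a describes the enrolment survey after the randomisation step.
2. Use the combined yes/no answer as a stratum in the primary rank test (van Elteren).
3. Report the responder analysis also without participants who answered yes.

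The SAP is written in the past tense, so data may already be in hand. If enrolment has closed, derive the pre-class dose trend from the enrolment and baseline medication data, if they allow it. Report the stratified and restricted analyses as sensitivity analyses beside the planned test. Readings taken after allocation are a further reason not to make them primary.

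The cost is a slightly longer survey, one stratified test and one extra table. The stratum relies on self-report, and misreporting gives back part of the gain (Step 3). Removing taperers also removes participants: in the Step 5 worst case, about 101 per arm remain and power is 58%, against 49% with them included and 62% with no tapering. Eligibility and clinical care do not change.
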